#### - Time course of the response of each treatment group

For fasting glucose and HbA1c, in order to evaluate the time course of the response of each treatment group, a MMRM will be performed as detailed in section 4.1.5.

In order to take into account multiplicity of tests, the ascending Hochberg procedure will be applied at each time point (see section 4.1.5 for details).

**Sensitivity analysis**

None

**Analysis by subgroups** (descriptive analysis only)

- By diabetic status (Yes, No) for fasting glucose, insulin, C-peptid, HOMA index, fructosamide and HbA1c
- By HbA1c at baseline ( $\leq 6.5\%$ ,  $>6.5\%$ ) for HbA1c

*5.2.3.9 Liver enzymes*

The following table describes for each parameter the collection time and the type of analyses to be done.

Parameter	Collection time	Main analyses (see section 5.2.3.8 describing the methodology)	Sensitivity analyses	Subgroup analyses
ALT	Screening, Baseline, weeks 4, 14, 24 and 28	Descriptive analysis Treatment effect ( each dose versus placebo ) Time course of the response of each treatment group	None	By diabetic status (Yes, No)
AST	Screening, Baseline, weeks 4, 14, 24 and 28	Descriptive analysis Treatment effect ( each dose versus placebo ) Time course of the response of each treatment group	None	By diabetic status (Yes, No)
GGT	Screening, Baseline, weeks 4, 14, 24 and 28	Descriptive analysis Treatment effect ( each dose versus placebo ) Time course of the response of each treatment group	None	By diabetic status (Yes, No)
Alkaline Phosphatase	Screening, Baseline, weeks 4, 14, 24 and 28	Descriptive analysis	None	By diabetic status (Yes, No)
Total Bilirubin	Screening, Baseline, weeks 4, 14, 24 and 28	Descriptive analysis	None	By diabetic status (Yes, No)

## 5.2.3.10 Plasma lipids levels

The following table describes for each parameter the collection time and the type of analyses to be done.

Parameter	Collection time	Main analyses (see section 5.2.3.8 describing the methodology)	Sensitivity analyses	Subgroup analyses
Total Cholesterol	Screening, Baseline, weeks 4, 14, 24 and 28	Descriptive analysis Treatment effect ( each dose versus placebo ) Time course of the response of each treatment group	None	By diabetic status (Yes, No) By Statins at baseline (Yes, No)
HDL-C	Screening, Baseline, weeks 4, 14, 24 and 28	Descriptive analysis Treatment effect ( each dose versus placebo ) Time course of the response of each treatment group	None	By diabetic status (Yes, No) By Statins at baseline (Yes, No)
LDL-C	Screening, Baseline, weeks 4, 14, 24 and 28	Descriptive analysis Treatment effect ( each dose versus placebo ) Time course of the response of each treatment group	None	By diabetic status (Yes, No) By Statins at baseline (Yes, No)
Triglycerides	Screening, Baseline, weeks 4, 14, 24 and 28	Descriptive analysis Treatment effect ( each dose versus placebo ) Time course of the response of each treatment group	None	By diabetic status (Yes, No) By Statins at baseline (Yes, No)
Apo A1	Baseline, week 24	Descriptive analysis Treatment effect ( each dose versus placebo )	None	By diabetic status (Yes, No) By Statins at baseline (Yes, No)
FFA	Baseline, week 24	Descriptive analysis	None	By diabetic status (Yes, No) By Statins at baseline (Yes, No)
Adiponectin	Baseline, week 24	Descriptive analysis Treatment effect ( each dose versus placebo )	None	By diabetic status (Yes, No) By Statins at baseline (Yes, No)
Leptin	Baseline, week 24	Descriptive analysis	None	By diabetic status (Yes, No) By Statins at baseline (Yes, No)
APO B	Baseline, week 24	Descriptive analysis	None	By diabetic status (Yes, No) By Statins at baseline (Yes, No)

Parameter	Collection time	Main analyses (see section 5.2.3.8 describing the methodology)	Sensitivity analyses	Subgroup analyses
APO C3	Baseline, week 24	Descriptive analysis	None	By diabetic status (Yes, No) By Statins at baseline (Yes, No)
FGF21	Baseline, week 24	Descriptive analysis	None	By diabetic status (Yes, No) By Statins at baseline (Yes, No)

Only fasting results will be considered for analyses.

For adiponectin, folds being defined as the value at week 24 divided by baseline value will also be presented in the descriptive analysis.

## 5.2.3.11 Efficacy inflammatory markers

The following table describes for each parameter the collection time and the type of analyses to be done.

Parameter	Collection time	Main analyses (see section 5.2.3.8 describing the methodology)	Sensitivity analyses	Subgroup analyses
Fibrinogen	Baseline, week 24	Descriptive analysis Treatment effect ( each dose versus placebo )	None	None
Hs-CRP	Baseline, week 24	Descriptive analysis Treatment effect ( each dose versus placebo )	None	None
alpha2 macroglobulin	Baseline, week 24	Descriptive analysis	None	None
Haptoglobin	Baseline, week 24	Descriptive analysis	None	None
IL-13	Baseline, week 24	Descriptive analysis	None	None
IL-17a	Baseline, week 24	Descriptive analysis	None	None
IL-6	Baseline, week 24	Descriptive analysis	None	None
IL-1b	Baseline, week 24	Descriptive analysis	None	None
TNF-a	Baseline, week 24	Descriptive analysis	None	None
INFg	Baseline, week 24	Descriptive analysis	None	None

## 5.2.3.12 Efficacy fibrosis markers

The following table describes for each parameter the collection time and the type of analyses to be done.

Parameter	Collection time	Main analyses (see section 5.2.3.8 describing the methodology)	Sensitivity analyses	Subgroup analyses
TIMP-1	Baseline, week 24	Descriptive analysis	None	None
TIMP-2	Baseline, week 24	Descriptive analysis	None	None
Hyaluronic acid	Baseline, week 24	Descriptive analysis	None	None
P3NP	Baseline, week 24	Descriptive analysis	None	None
NFS	Baseline, week 24	Descriptive analysis Treatment effect ( each dose versus placebo )	None	None
FIB-4 score	Baseline, week 24	Descriptive analysis Treatment effect ( each dose versus placebo )	None	None
ELF score	Baseline, week 24	Descriptive analysis Treatment effect ( each dose versus placebo )	None	None
MACK-3	Baseline, week 24	Descriptive analysis Treatment effect ( each dose versus placebo )	None	None
FIBC3	Baseline, week 24	Descriptive analysis Treatment effect ( each dose versus placebo )	None	None
ABC3D	Baseline, week 24	Descriptive analysis Treatment effect ( each dose versus placebo )	None	None
Cytokeratin M30	Baseline, week 24	Descriptive analysis	None	None
Cytokeratin M65	Baseline, week 24	Descriptive analysis	None	None
MMP2	Baseline, week 24	Descriptive analysis	None	None
MMP9	Baseline, week 24	Descriptive analysis	None	None
Pro-C3	Baseline, week 24	Descriptive analysis Treatment effect ( each dose versus placebo )	None	None

The following variables will also be described qualitatively over time using descriptive statistics by treatment group and diabetic status

- ELF score (No to mild fibrosis, moderate fibrosis, severe fibrosis, cirrhosis)
- NFS (Low probability of fibrosis F3-F4, Intermediate, High probability of fibrosis F3-F4)
- FIB-4 score (Low probability of fibrosis F3-F4, Intermediate, High probability of fibrosis F3-F4)
- MACK-3 score (No fibrosis, Fibrosis undefinable (grey zone), Fibrosis)

Moreover, as an exploratory analysis, the ELF score in class, the NFS in class and the FIB-4 score in class will be cross-tabulated with the CRN-F score (F0-F1, F2-F3): at baseline and then

at Week 24, regardless of treatment group. Similarly, the MACK-3 score in class will be cross-tabulated with the CRN-F score (F0, F1, F2, F3).

The ProC3, FIBC3 and ABC3D values will be described in each modality of the CRN-F score (F0-F1, F2-F3): at baseline and then at Week 24, regardless of treatment group.

### 5.2.3.13 Efficacy chemistry markers

The following table describes for each parameter the collection time and the type of analyses to be done.

Parameter	Collection time	Main analyses (see section 5.2.3.8 describing the methodology)	Sensitivity analyses	Subgroup analyses
Plasma Iron	Screening, week 24	Descriptive analysis	None	None
Transferrin	Screening, week 24	Descriptive analysis	None	None
Ferritin	Screening, week 24	Descriptive analysis	None	None

#### 5.2.3.14 Improvement of ISHAK fibrosis by at least 2 stages with no worsening of NASH

The endpoints will be a binary variable (responder / non responder) based on the change from baseline to Week 24 of the ISHAK-F score and the worsening of NASH (see section 4.5.4.1.12).

#### **Main analysis**

The population of analysis will be the FAS as described in section 4.3.3. The primary imputation method described in section 4.1.6.3 will be used for missing data replacement.

##### - Descriptive analysis

The number (% with its 95% confidence interval) of responders and non-responders at Week 24 will be summarized in a table using descriptive statistics by treatment group and diabetic status.

The reason for non-response (Worsening of CRN-S score,  $\pm$  Worsening of CRN-I score,  $\pm$  Worsening of CRN-B score,  $\pm$  No improvement of 2 stages in ISHAK-F score, No post-treatment biopsy available) will also be displayed.

##### - Evaluation of treatment effect (each dose versus placebo)

The same methodology as the one defined in the section 5.2.2.1 (paragraph ‘Evaluation of treatment effect (each dose versus placebo)’ ) will be implemented.

##### - Dose-response relationship

Moreover, the dose-response relationship will be assessed on the FAS (Primary imputation method and Observed cases under treatment), and on the PP (Observed cases under treatment) according to method detailed in section 4.1.5 (Cochran-Armitage test using PROC LOGISTIC with adjustment on diabetic status).

#### **Sensitivity analyses**

Several sensitivity analyses will be performed as detailed in table below. Each time, descriptive analysis, evaluation of treatment effect (each dose versus placebo) will be performed as detailed above for main analysis.

Analysis population	Treatment group	Missing data replacement
FAS	Actual treatment received	Observed cases under treatment*
PP	Actual treatment received	Observed cases under treatment

\* This analysis corresponds to analyses on completers (biopsy at week 24 performed, within maximum 14 days after last intake).

### 5.3 Safety data

#### 5.3.1 *Extent of exposure*

The following parameters will be summarized in a table using descriptive statistics by treatment group in the safety set of patients:

- Treatment prematurely discontinued during study (Yes, No)
- Treatment duration (weeks)
- Overall persistence (%)
- Overall compliance at time of biopsy at week 24 (%)
- Overall compliance at time of biopsy at week 24 (%) based on lanifibranor bottles
- Compliance (%) at each visit

#### 5.3.2 *Display of adverse events*

##### 5.3.2.1 *Overall summary of Treatment Emergent Adverse Events (TEAEs)*

The following summary statistics will be given in the safety set of patients by treatment group (Lanifibranor 800mg, lanifibranor 1200mg, lanifibranor all, placebo):

- Number (%) of patients with at least one **TEAE**
- Number (%) of patients with at least one **TEAE related to treatment**
- Number (%) of patients with at least one **TESAE**
- Number (%) of patients with at least one **TESAE related to treatment**
  
- Number (%) of patients with a **fatal TESAE**
- Number (%) of patients with a **fatal TESAE related to treatment**
  
- Number (%) of patients with at least one **mild TEAE**
- Number (%) of patients with at least one **moderate TEAE**
- Number (%) of patients with at least one **severe TEAE**
  
- Number (%) of patients with at least one **severe TEAE related to treatment**
- Number (%) of patients with at least one **severe TESAE**
- Number (%) of patients with at least one **severe TESAE related to treatment**
  
- Number (%) of patients with at least one **TEAE leading to treatment permanent discontinuation**
- Number (%) of patients with at least one **TEAE leading to treatment permanent discontinuation related to treatment**

Corresponding number of events will also be provided for each type of AEs.

### 5.3.2.2 Overall Analysis of Treatment Emergent Adverse Events (TEAEs)

The number (%) of patients with at least one **TEAE** (and the corresponding number of events) will be described by **SOC and PT** by treatment group in the safety set of patients. In case a same patient presented the same AE (i.e. same AE as defined according to SOC and PT) several times during the study, only one occurrence per patient will be reported, but the total number of events will be given.

Same tables as this one will also be produced for:

- **TEAE related to treatment**
- **TESAE**
- **TESAE related to treatment**
- **Fatal TESAE**
- **Severe TEAE**
- **Severe TEAE related to treatment**
- **Severe TESAE**
- **Severe TESAE related to treatment**
- **TEAE leading to treatment permanent discontinuation**
- **TEAE leading to treatment permanent discontinuation related to treatment**

### 5.3.2.3 Analysis of Non-Treatment Emergent Adverse Events (non-TEAEs)

For Non-TEAEs, only a listing will be edited in the safety set of patients.

### 5.3.2.4 Analysis of Post-Treatment Adverse Events (PTAEs)

For PTEAEs, only a listing will be edited in the safety set of patients.

### 5.3.2.5 Analysis of Adverse Events in screen failure patients

A listing of all AEs experienced in screen failure patients will be edited.

## 5.3.3 Other safety analysis

### 5.3.3.1 Specific cardiac inflammatory safety: NT-pro-BNP

The population of analysis will be the Safety Set as described in section 4.3.3. Only the observed cases under treatment will be analysed (see section 4.1.6.3).

The NT-pro-BNP is collected at baseline and week 24. A listing of abnormal values at Baseline and/or Week 24 will be provided including absolute and relative changes from baseline.

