#### 1.4.3 Toxicology

Lanifibranor has a very low acute toxicity (maximal non-lethal dose of 2000 mg/kg in rodents) and is not irritating to the skin.

Lanifibranor is devoid of genotoxic potential in the full international conference on harmonization (ICH) battery of genotoxicity assays. The three major human metabolites, IV1197736, IV1197347 and IV1537661, were also found devoid of genotoxic potential in a bacterial reverse mutation test and a mammalian cell assay.

Lanifibranor is devoid of deleterious effects on vital functions such as cardiovascular, central and autonomic nervous system and respiratory system. In a 9-week head-to-head comparative study in rats aimed at evaluating side effects of PPAR agonists such as plasma volume expansion and secondary cardiac hypertrophy, or skeletal muscle toxicity, daily doses of lanifibranor up to 1000 mg/kg compared favorably with other PPAR agonists rosiglitazone, muraglitazar and tesaglitazar. These observations were substantiated in repeated dose toxicity studies with lanifibranor in rats and monkeys.

No potential risks have been identified from pivotal toxicology studies with lanifibranor in rat and in monkey and segment II reproductive toxicity studies in rats and rabbits. All treatment-related findings (i.e. liver, bone marrow, adipose tissue) were reversible.

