### **6.3 Safety Variables**

All safety variables will be primary ones. Safety evaluations will be completed as given in section 9.7 and as indicated below.

The Investigator will rate all safety variables as to clinical relevance or not. In case of a clinically relevant abnormality, the safety evaluation will be repeated. If the abnormality is confirmed and clinically relevant, it will be recorded as an AE term in the eCRF. The abnormality will be followed up until the value has returned to normal or an adequate explanation is found.

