**Table 7 : Central laboratory tests for safety assessment**

Domain	Goal	Test	Screen	V0	V1	V2	V3	V4
Bone	Safety	B-Crosslaps	-	✓	-	-	✓	-
	Safety	Osteocalcin	-	✓	-	-	✓	-
Chemistry	Safety	Creatinine	✓	✓	✓	✓	✓	✓
	Safety	CPK	✓	✓	✓	✓	✓	✓
	Safety	Urea	✓	✓	✓	✓	✓	✓
	Safety	Albumin	✓	✓	✓	✓	✓	✓
Hematology	Safety	Hb	✓	✓	✓	✓	✓	✓
	Safety	RBC	✓	✓	✓	✓	✓	✓
	Safety	Platelets	✓	✓	✓	✓	✓	✓
	Safety	WBC (Diff Count)	✓	✓	✓	✓	✓	✓
	Safety	MCV	✓	✓	✓	✓	✓	✓
	Safety	CCMH	✓	✓	✓	✓	✓	✓
	Safety	Hematocrit	✓	✓	✓	✓	✓	✓
	Safety	Reticulocytes	✓	✓	✓	✓	✓	✓
Inflammation	Safety	Nt-ProBNP	-	✓	-	-	✓	-
liver	Safety	INR	✓	✓	✓	✓	✓	✓

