#### 9.7.3 *Other Observations Related to Safety*

### - **Laboratory tests**

The analysis will include patients exposed to study medication who have at least one laboratory test performed after the first study product intake and, when required by the definition of the abnormality, with an available baseline value and available normal ranges. For these descriptions, the baseline value will be the latest available measure before the first study product dose intake. International units will be used in all listings, tables and graphs. Results and changes from baseline of laboratory parameters will be summarized by mean, standard deviation, median, minimum and maximum at each time point and for the final on-treatment visit. Unscheduled and/or repeated results will only be listed and not summarized.

Shift tables and other tabular and graphical methods will be used to present the results for tests of interest. Listings will be provided with flags indicating clinically significant out-of-range values, clinically non-significant out-of-range values.

In addition, out-of-range values will be assessed by the investigator as clinically significant or not clinically significant. Abnormal laboratory tests assessed by the investigator as clinically significant will be reported as an AE.

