### **Main analysis**

The population of analysis will be the Safety Set as described in section 4.3.4. Only the observed cases under treatment will be analysed (see section 4.1.6.3).

- Descriptive analysis

Each parameter will be described at each study visit using descriptive statistics by treatment group in the safety set of patients, in terms of:

- Raw values
- Absolute change from Baseline
- Status over time (Normal-Normal, Normal-Abnormal, Abnormal-Normal, Abnormal-Abnormal)

Then, for each parameter, will be provided a graph reporting the mean (95% CI) of the parameter by visit and treatment group.

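### NT-proBNP, a cardiac safety marker, is the only protocol Table 7 safety laboratory test without a descriptive summary in the SAP, and SAP 4.6 does not declare the departure

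*SAP*

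**What the plan says.** **Protocol.** NT-proBNP appears in Table 7, titled "Central laboratory tests for safety assessment", with measurements at V0 and V3. Section 6.3 gives safety variables high standing: "All safety variables will be primary ones". For laboratory tests, section 9.7.3 states: "Results and changes from baseline of laboratory parameters will be summarized by mean, standard deviation, median, minimum and maximum at each time point". The same sentence also asks for a summary at the final on-treatment visit. It continues: "Shift tables and other tabular and graphical methods will be used to present the results for tests of interest".

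**SAP.** Section 5.3.3.1 confirms the two measurements ("The NT-pro-BNP is collected at baseline and week 24") and limits the data to observed cases under treatment. The whole planned output is then: "A listing of abnormal values at Baseline and/or Week 24 will be provided including absolute and relative changes from baseline". The 5.3.3.3 parameter list does not contain NT-proBNP. For the tests that are on that list the plan reads: "Each parameter will be described at each study visit using descriptive statistics by treatment group in the safety set of patients, in terms of". Three displays are then named, covering the measured value, its absolute change and the normal/abnormal status over time, and a graph by visit and arm is added. Section 4.6 lists modifications from the protocol's statistical section and does not mention NT-proBNP.

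**The concern.** A listing restricted to abnormal values says nothing about patients whose values rise but stay within range. It also has no denominator, so the proportion of patients becoming abnormal in each arm is not a planned output. A descriptive table by arm supplies both.

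The marker was not chosen at random. Protocol 1.4.3 describes a rat study "aimed at evaluating side effects of PPAR agonists such as plasma volume expansion and secondary cardiac hypertrophy", and the text under Tables 3 and 4 counts the heart among the known target organs of PPAR-agonist toxicity. Exclusion criterion 16 removes patients with a cardiovascular event or dysrhythmia. It is therefore plausible, though this is my inference, that most values will lie within range, which is where an abnormal-only listing shows nothing.

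**Working it through.** No figure in the plan is in dispute, so the check is a comparison of texts.

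1. **Does the protocol rule cover NT-proBNP?** Table 7 gives its goal as safety and places it with the central-laboratory tests. Section 9.7.3 applies to laboratory parameters without exception. It does.

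2. **How does the SAP treat each Table 7 test?**
   - Haematology, 8 tests (Hb, RBC, platelets, WBC with differential, MCV, MCHC, haematocrit, reticulocytes): descriptive summary in SAP 5.3.3.3.
   - Chemistry, 4 tests (creatinine, CPK, urea, albumin): descriptive summary in SAP 5.3.3.3.
   - INR, 1 test: descriptive summary in SAP 5.3.3.3.
   - Bone markers, 2 tests (B-Crosslaps, osteocalcin): descriptive analysis in SAP 5.3.3.2.
   - NT-proBNP, 1 test: listing of abnormal values in SAP 5.3.3.1.

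   Total: 8 + 4 + 1 + 2 + 1 = 16. Summarised: 13 + 2 = 15. Listing only: 1.

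3. **Does the sampling schedule explain it?** No. The bone markers are taken at the same two visits and are still described.

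4. **Is the departure declared?** SAP 4.6.1 to 4.6.6 cover terminology, populations, endpoints, efficacy analysis, subgroups and liver iron content. The last of these shows that a change to a single laboratory variable was thought worth recording. NT-proBNP is absent.

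5. **Does the precedence clause settle it?** Protocol 9.7.4 lets a clarification in the SAP prevail over other readings of the protocol. Replacing a required summary with a listing is a change of output, not a clarification of one.

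6. **Which values reach the display?** Under SAP 4.1.6.3, values taken more than 3 days after last intake count as missing, and a V3 held for early discontinuation is left out of Week 24 descriptions. Protocol 5.3.4 asks withdrawn patients to have the V3 assessments if possible, and protocol 10.1 includes deterioration in cardiac status among the reasons for withdrawal. Values from such patients could therefore be collected and not shown.

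7. **Cross-reference.** SAP 5.3.3.1 cites section 4.3.3 for the Safety Set. Section 4.3.3 defines the FAS; the Safety Set is in 4.3.4.

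**The case against.** Several points on the other side have force.

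- **NT-proBNP is not the only relevant safety measure.** The SAP summarises by arm the centrally read ECG status, QTcF and heart rate (5.3.3.5), CPK, haemoglobin and haematocrit (5.3.3.3), weight and blood pressure (5.3.3.4), and TEAEs by SOC and PT (5.3.2.2). A reader might infer that cardiac safety goes unexamined. The documents do not support that.
- **Abnormal cases could be counted.** If the listing shows treatment arm, a reader can tally new abnormalities by hand. What is missing is a planned count with a denominator. Only the within-range shift is wholly lost.
- **There are other routes.** Abnormalities judged clinically significant are reported as AEs (protocol 6.3 and 9.7.3) and so reach the TEAE tables. This route is uncertain, because protocol 6.3.2 blinds some laboratory values without naming them. The DSMB also sees main laboratory assessments by coded arm (protocol 6.4.3). Neither route gives a summary of the marker in the final analysis.
- **The compound's own data are reassuring.** In the rat study lanifibranor did better than the comparator PPAR agonists, and protocol 1.4.4 reports no clinically relevant changes in cardiac markers in earlier human studies. The completed studies described there dosed for at most 4 weeks, against 24 weeks here. A reader should not infer a known cardiac signal; the case for the table is that the trial should be able to show the data either way.
- **The on-treatment restriction is not peculiar to NT-proBNP.** SAP 5.3.3.3 applies it to its laboratory tests too, so moving the marker there would not remove it.
- **The sources are incomplete.** The SAP was written to protocol v5.1, and the protocol available is v5.0. The appended table mock-ups are not available. Either could contain an explanation, but SAP 4.6, where one would be expected, has none.

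**Conclusion.** The point stands as an undeclared reduction of one descriptive safety output: 1 of 16 Table 7 tests has no summary by arm, against an explicit requirement in protocol (v5.0) 9.7.3. The consequences are that a within-range shift between arms would not be visible and that no count or denominator of newly abnormal patients by arm is planned.

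A reader might want to express this as a detectable difference or a loss of power. The documents do not support such a figure. They give no NT-proBNP mean, SD or abnormal rate, and the table that the protocol requires is descriptive, so power is not a property of it.

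The conclusion assumes that protocol v5.1 did not alter the laboratory section of 9.7.3 and that the mock-ups do not already contain the missing table. It does not touch the primary endpoint. It is worth correcting because safety is part of the stated objective and the correction is cheap.

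**What to change.** 1. Add NT-proBNP to the SAP 5.3.3.3 descriptive analysis, by arm in the Safety Set: raw value, absolute and relative change from baseline, and normal/abnormal status over time with denominators. The SAP's standard statistics (4.1.4) already include median and quartiles, and 4.5.1 already defines relative change and the status categories.
2. Show early-termination V3 values alongside Week 24, labelled as such, since the on-treatment rule in 5.3.3.3 would otherwise exclude them.
3. Keep the listing of abnormal values and include treatment arm in it.
4. Correct the Safety Set reference in 5.3.3.1 from 4.3.3 to 4.3.4.
5. If the sponsor prefers the listing alone, declare the departure in SAP 4.6 and give the reason.

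The cost is one standard table with its graph and a few lines of SAP text. No new data, visits or tests are needed.
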